## 14.2. CONCOMITANT MEDICATIONS/VACCINATIONS (ALLOWED & PROHIBITED)

Medications or vaccinations specifically prohibited in the exclusion criteria are not allowed during the ongoing study. If there is a clinical indication for one of these or other medications or vaccinations specifically prohibited during the study, discontinuation from study therapy may be required. The investigator should discuss any questions regarding this with the Study Chair. The final decision on any supportive therapy or vaccination rests with the investigator and/or the patient's primary physician. However, the decision to continue the patient on study therapy or vaccination schedule requires the mutual agreement of the Study Chair, AFT, and the patient.

### 14.2.1. Acceptable Concomitant Medications

All treatments that the investigator considers necessary for a patient's welfare may be administered at the discretion of the investigator in keeping with the community standards of medical care. All concomitant medication will be recorded on the case report form (CRF) including all prescription, over-the-counter (OTC), herbal supplements, and IV medications and fluids. If changes occur during the study

period, documentation of drug dosage, frequency, route, and date may also be included on the CRF.

All concomitant medications received within 28 days before the first dose of study treatment and 30 days after the last dose of study treatment should be recorded. Concomitant medications administered after 30 days after the last dose of study treatment should be recorded if administered due to a severe adverse event (SAE) or SAEs and/or event of clinical interest, as defined in Section 17.2.2.

#### **14.2.2. Prohibited Concomitant Medications**

Patients are prohibited from receiving the following therapies during the screening and treatment Phase of this study:

- Anti-cancer systemic chemotherapy or biological therapy
- Immunotherapy not specified in this protocol
- Chemotherapy not specified in this protocol
- Investigational agents other than pembrolizumab (MK-3475)
- Radiation therapy
  - Note: Radiation therapy to a symptomatic, non-target solitary lesion or to the brain may be allowed after consultation with the Study PI and Sponsor
- Live vaccines within 30 days prior to the first dose of study treatment and while participating in the study. Examples of live vaccines include, but are not limited to, the following: measles, mumps, rubella, chicken pox, yellow fever, rabies, BCG, and typhoid (oral) vaccine. Seasonal influenza vaccines for injection are generally killed virus vaccines and are allowed; however intranasal influenza vaccines (e.g. Flu-Mist®) are live attenuated vaccines, and are not allowed.
- Immunosuppressive medications including, but not limited to systemic corticosteroids (>10 mg/day prednisone or equivalent), methotrexate, azathioprine, and tumor necrosis factor alpha (TNF- $\alpha$ ) blockers. Use of immunosuppressive medications for the management of investigational product-related AEs and in subjects with contrast allergies. The use of physiologic steroid replacement may be approved after consultation with the investigator and Study PI. In addition, use of inhaled and intranasal corticosteroids is permitted. The use of physiologic doses of corticosteroids may be approved after consultation with the Sponsor.
- Systemic glucocorticosteroids for any other purpose other than to modulate symptoms from an event of clinical interest or for use as a pre-medication prior to a CT scan for subjects with contrast allergy or

for use for COPD exacerbation requiring steroid for recovery. Replacement doses of steroids (for example, prednisone 5-7.5 mg daily) are permitted while on study. Inhaled corticosteroids are allowed.

Patients who, in the assessment by the investigator, require the use of any of the aforementioned treatments for clinical management should be removed from the study.

The Exclusion Criteria describes other medications which are prohibited in this study.

There are no prohibited therapies during the Post-Treatment Follow-up Phase.

### 14.3. RESCUE MEDICATIONS AND SUPPORTIVE CARE

#### 14.3.1. Supportive Care Guidelines for Pembrolizumab

Patients should receive appropriate supportive care measures as deemed necessary by the treating investigator, including but not limited to the items outlined below:

**Diarrhea:** Patients should be carefully monitored for signs and symptoms of enterocolitis (such as diarrhea, abdominal pain, blood or mucus in stool, with or without fever) and of bowel perforation (such as peritoneal signs and ileus). In symptomatic patients, infectious etiologies should be ruled out, and if symptoms are persistent and/or severe, endoscopic evaluation should be considered.

- All patients who experience diarrhea/colitis should be advised to drink liberal quantities of clear fluids. If sufficient oral fluid intake is not feasible, fluid and electrolytes should be substituted via IV infusion.
- In patients with moderate enterocolitis (Grade 2), pembrolizumab (MK-3475) should be withheld and anti-diarrheal treatment should be started. If symptoms are persistent for more than one week, systemic corticosteroids should be initiated (e.g., 0.5 mg/kg/day of prednisone or equivalent). When symptoms improve to Grade 1 or less, corticosteroid taper should be started and continued over at least one month.
- In patients with severe enterocolitis (Grade 3), pembrolizumab (MK-3475) will be permanently discontinued and treatment with systemic corticosteroids should be initiated (1 to 2 mg/kg/day of prednisone or equivalent). Prophylactic antibiotics should be initiated for opportunistic infections. When symptoms improve to Grade 1 or less, corticosteroid taper should be started and continue over at least 1 month.

**Nausea/vomiting:** Nausea and vomiting should be treated aggressively, and consideration should be given in subsequent cycles to the

administration of prophylactic antiemetic therapy according to standard institutional practice. Patients should be strongly encouraged to maintain liberal oral fluid intake.

**Anti-infectives:** Patients with a documented infectious complication should receive oral or IV antibiotics or other anti-infective agents as considered appropriate by the treating investigator for a given infectious condition, according to standard institutional practice.

**Immune-related adverse events:** Please see Section 13.3.1.3. below regarding diagnosis and management of adverse experiences of a potential immunologic etiology.

**Management of Infusion Reactions:** Acute infusion reactions (which can include cytokine release syndrome, angioedema, or anaphylaxis) are different from allergic/hypersensitive reactions, although some of the manifestations are common to both AEs. Signs and symptoms usually develop during or shortly after drug infusion and generally resolve completely within 24 hours of completion of infusion. Signs/symptoms may include: Allergic reaction/hypersensitivity (including drug fever); Arthralgia (joint pain); Bronchospasm; Cough; Dizziness; Dyspnea (shortness of breath); Fatigue (asthenia, lethargy, malaise); Headache; Hypertension; Hypotension; Myalgia (muscle pain); Nausea; Pruritis/itching; Rash/desquamation; Rigors/chills; Sweating (diaphoresis); Tachycardia; Tumor pain (onset or exacerbation of tumor pain due to treatment); Urticaria (hives, welts, wheals); Vomiting.

Table 8 below shows treatment guidelines for patients who experience an infusion reaction associated with administration of pembrolizumab (MK-3475).

**Table 8: Infusion Reaction Treatment Guidelines**

NCI CTCAE Grade	Treatment	Premedication at Subsequent Dosing
Grade 1 Mild reaction; infusion interruption not indicated; intervention not indicated	Increase monitoring of vital signs as medically indicated until the subject is deemed medically stable in the opinion of the investigator.	None
Grade 2 Requires infusion interruption but responds promptly to symptomatic treatment (e.g., antihistamines, NSAIDs, narcotics, IV fluids); prophylactic medications indicated for < =24 hrs	Stop the infusion and monitor symptoms.  Additional appropriate medical therapy may include but is not limited to: 
 
▪ IV fluids
 
▪ Antihistamines
 
▪ NSAIDs
 
▪ Acetaminophen
 
▪ Narcotics
 
 Increase monitoring of vital signs as medically indicated until the subject is deemed medically stable in the opinion of the investigator.	Patient may be premedicated 1.5h (± 30 minutes) prior to infusion of pembrolizumab with: 
 
▪ Diphenhydramine 50 mg po (or equivalent dose of antihistamine).
 
▪ Acetaminophen 500-1000 mg po (or equivalent dose of antipyretic).
 

NCI CTCAE Grade	Treatment	Premedication at Subsequent Dosing
	
If symptoms resolve within one hour of stopping drug infusion, the infusion may be restarted at 50% of the original infusion rate (e.g., from 100 mL/hr to 50 mL/hr). Otherwise dosing will be held until symptoms resolve and the subject should be premedicated for the next scheduled dose.
 
Patients who develop Grade 2 toxicity despite adequate premedication should be permanently discontinued from further study treatment administration.
	

Grades 3 or 4 Grade 3: Prolonged (i.e., not rapidly responsive to symptomatic medication and/or brief interruption of infusion); recurrence of symptoms following initial improvement; hospitalization indicated for other clinical sequelae (e.g., renal impairment, pulmonary infiltrates) Grade 4: Life-threatening; pressor or ventilatory support indicated
	
Stop Infusion. Additional appropriate medical therapy may include but is not limited to:
 
 
▪ IV fluids
 
▪ Antihistamines
 
▪ NSAIDS
 
▪ Acetaminophen
 
▪ Narcotics
 
▪ Oxygen
 
▪ Pressors
 
▪ Corticosteroids
 
▪ Epinephrine
 
 
Increase monitoring of vital signs as medically indicated until the subject is deemed medically stable in the opinion of the investigator.
 
Hospitalization may be indicated.
 
Patient is permanently discontinued from further study treatment administration.
	
No subsequent dosing

Appropriate resuscitation equipment should be available in the room and a physician readily available during the period of drug administration. For Further information, please refer to the Common Terminology Criteria for Adverse Events v4.0 (CTCAE) at http://ctep.cancer.gov
		

**14.3.2. Supportive Care Guidelines for Pneumonitis**

Patients with symptomatic pneumonitis should immediately stop receiving pembrolizumab and have an evaluation. The evaluation may include bronchoscopy and pulmonary function tests to rule out other causes such as infection. If the patient is determined to have study drug associated pneumonitis, the suggested treatment plan is detailed in Table 9.

**Table 9. Recommended Approach to Handling Pneumonitis**

Study Drug Associated Pneumonitis	Withhold/Discontinue Pembrolizumab (MK-3475)?	Supportive Care
Grade 1 (asymptomatic)	No action	Intervention not indicated
Grade 2	Withhold pembrolizumab (MK-3475), may return to treatment if improves to Grade 1 or resolves within 6 weeks	Systemic corticosteroids are indicated. Taper if necessary.
Grade 3 and Grade 4	Discontinue pembrolizumab (MK-3475)	Systemic corticosteroids are indicated. The use of infliximab may be indicated as appropriate. Refer to the Events of Clinical Interest and Immune-related Adverse Event Guidelines in Section 13.3.3 below for additional recommendations.

For Grade 2 pneumonitis that improves to  $\leq$  Grade 1 within 6 weeks, the following rules should apply:

- For the first episode of pneumonitis
  - May increase dosing interval by one week in subsequent cycles
- For the second episode of pneumonitis
  - Permanently discontinue pembrolizumab if upon rechallenge, the patient develops pneumonitis  $\geq$  Grade 2

#### **14.3.3. Supportive Care Guidelines for Events of Clinical Interest/Immune Related Adverse Events (IRAEs)**

Events of clinical interest of a potential immunologic etiology (IRECs) may be defined as an adverse event of unknown etiology, associated with drug exposure and is consistent with an immune phenomenon. IRAEs may be predicted based on the nature of the pembrolizumab (MK-3475) compound, its mechanism of action, and reported experience with immunotherapies that have a similar mechanism of action. Special attention should be paid to AEs that may be suggestive of potential IRAEs. An IRAE can occur shortly after the first dose or several months after the last dose of treatment.

If an IRAE is suspected, efforts should be made to rule out neoplastic, infectious, metabolic, toxin or other etiologic causes prior to labeling an adverse event as an IRAE. Patients who develop a Grade 2 or higher IRAE should be discussed immediately with the Study PI.

Recommendations to managing IRAEs not detailed elsewhere in the protocol are detailed in Table 10.

**Table 10. General Approach to Treating IRAEs**

IRAE	Withhold/Discontinue Pembrolizumab?	Supportive Care
Grade 1	No action	Provide symptomatic treatment
Grade 2	May withhold pembrolizumab (MK-3475)	Consider systemic corticosteroids in addition to appropriate symptomatic treatment
Grade 3 and Grade 4	Withhold pembrolizumab (MK-3475) Discontinue if unable to reduce corticosteroid dose to < 10 mg per day prednisone equivalent within 6 weeks of toxicity	Systemic corticosteroids are indicated in addition to appropriate symptomatic treatment, utilizing 1 to 2 mg/kg prednisone or equivalent per day.  Steroid taper should be considered once symptoms improve to Grade 1 or less and tapered over at least 4 weeks.

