## 14. DOSE AND TREATMENT MODIFICATIONS (ESCALATION/TITRATION/OTHER), CONCOMITANT MEDICATIONS, SUPPORTIVE CARE

### 14.1. DOSE MODIFICATION

#### 14.1.1. Pembrolizumab (MK-3475) Dose Modification

Adverse events (both non-serious and serious) associated with pembrolizumab (MK-3475) exposure may represent an immunologic etiology. These adverse events may occur shortly after the first dose or several months after the last dose of treatment. Pembrolizumab dosing may continue in the event of an unrelated or grade 1 adverse event. Pembrolizumab (MK-3475) must be withheld for drug-related toxicities and severe or life-threatening adverse events, as per Table 5 below. Drug-related toxicities are managed by dose delay or interruption rather than dose reduction. See Section 14.3.1 for supportive care guidelines, including use of corticosteroids.

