**Table 5. Dose Modification Guidelines for Pembrolizumab Drug-Related Adverse Events**

Toxicity	Hold Treatment For Grade	Timing for Restarting Treatment	Treatment Discontinuation
Diarrhea/Colitis	2-3	Toxicity resolves to Grade 0-1	Toxicity does not resolve within 6 weeks of last dose or inability to reduce corticosteroid to 10 mg or less of prednisone or equivalent per day within 6 weeks
	4	Permanently discontinue	Permanently discontinue
AST, ALT, or Increased Bilirubin	2	Toxicity resolves to Grade 0-1	Toxicity does not resolve within 6 weeks of last dose
	3-4	Permanently discontinue (see exception below) 	Permanently discontinue
Type 1 diabetes mellitus (if new onset) or Hyperglycemia	T1DM or 3-4	Hold pembrolizumab for new onset Type 1 diabetes mellitus or Grade 3-4 hyperglycemia associated with evidence of beta cell failure	Resume pembrolizumab when patients are clinically and metabolically stable, yet discontinue treatment if patients are not improved within 6 weeks of last dose
Hypophysitis	2-4	Toxicity resolves to Grade 0-1 Therapy with pembrolizumab can be continued while endocrine replacement therapy is instituted	Toxicity does not resolve within 6 weeks of last dose or inability to reduce corticosteroid to 10 mg or less of prednisone or equivalent per day within 6 weeks
Hyperthyroidism	3	Toxicity resolves to Grade 0-1	Toxicity does not resolve within 6 weeks of last dose or inability to reduce corticosteroid to 10 mg or less of prednisone or equivalent per day within 6 weeks
	4	Permanently discontinue	Permanently discontinue
Hypothyroidism		Therapy with pembrolizumab can be continued while thyroid replacement therapy is instituted	Therapy with pembrolizumab can be continued while thyroid replacement therapy is instituted
Infusion Reaction	2 b	Toxicity resolves to Grade 0-1	Permanently discontinue if toxicity develops despite adequate premedication
	3-4	Permanently discontinue	Permanently discontinue
Pneumonitis	2	Toxicity resolves to Grade 0-1	Toxicity does not resolve within 6 weeks of last dose or inability to reduce corticosteroid to 10 mg or less of

Toxicity	Hold Treatment For Grade	Timing for Restarting Treatment	Treatment Discontinuation
			prednisone or equivalent per day within 6 weeks.
	3-4	Permanently discontinue	Permanently discontinue

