Renal Failure or Nephritis	2	Toxicity resolves to Grade 0-1	Toxicity does not resolve within 6 weeks of last dose or inability to reduce corticosteroid to 10 mg or less of prednisone or equivalent per day within 6 weeks
	3-4	Permanently discontinue	Permanently discontinue
All Other Drug-Related Toxicity, excluding hematologic toxicity	3 or Severe	Toxicity resolves to Grade 0-1	Toxicity does not resolve within 6 weeks of last dose or inability to reduce corticosteroid to 10 mg or less of prednisone or equivalent per day within 6 weeks
	4	Permanently discontinue	Permanently discontinue
Hematologic Toxicity			
Thrombocytopenia associated with bleeding	3	Toxicity resolves to Grade 0-1 or baseline May increase the dosing interval by 1 week	Toxicity does not resolve within 6 weeks of last dose Permanently discontinue if associated with severe or life threatening bleeding event
Neutropenia, anemia, or thrombocytopenia	4	Toxicity resolves to Grade 0-1 or baseline May increase the dosing interval by 1 week	Toxicity does not resolve within 6 weeks of last dose Permanently discontinue if associated with any severe or life threatening event
Note: Permanently discontinue for any severe or Grade 3 drug-related AE that recurs or any life-threatening event.			
 For patients with liver metastasis who begin treatment with Grade 2 AST or ALT, if AST or ALT increases by greater than or equal to 50% relative to baseline and lasts for at least 1 week then patients should be discontinued.			
 If symptoms resolve within one hour of stopping drug infusion, the infusion may be restarted at 50% of the original infusion rate (e.g., from 100 mL/hr to 50 mL/hr). Otherwise dosing will be held until symptoms resolve and the subject should be premedicated for the next scheduled dose: Refer to Table 8 Infusion Treatment Guidelines for further management details.			
 Patients with intolerable or persistent Grade 2 drug-related AE may hold study medication at physician discretion. Permanently discontinue study drug for persistent Grade 2 adverse reactions for which treatment with study drug has been held, that do not recover to Grade 0-1 within 6 weeks of the last dose.			

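### For a Grade 4 immune-related event without its own row in Table 5, Table 5 ends pembrolizumab permanently but Table 10 only withholds it

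*Combined protocol and SAP*

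**What the plan says.** Section 14.1.1 introduces Table 5 in mandatory terms: "Pembrolizumab (MK-3475) must be withheld for drug-related toxicities and severe or life-threatening adverse events, as per Table 5 below". Toxicities without their own row fall into the row headed "All Other Drug-Related Toxicity, excluding hematologic toxicity". That row allows a hold and restart for Grade 3 or severe events. Its stopping grounds at that grade begin: "Toxicity does not resolve within 6 weeks of last dose or inability to reduce corticosteroid to 10 mg or less of prednisone". For Grade 4, both the restart column and the discontinuation column call for permanent discontinuation. The note under the table adds: "Permanently discontinue for any severe or Grade 3 drug-related AE that recurs or any life-threatening event".

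Section 14.3.3 then presents Table 10 as recommendations for immune-related events that the protocol does not detail elsewhere. Its last row covers Grades 3 and 4 together. The action is to withhold pembrolizumab, followed by: "Discontinue if unable to reduce corticosteroid dose to < 10 mg per day prednisone equivalent within 6 weeks of toxicity". The row names no other ground for stopping and does not separate Grade 4 from Grade 3.

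**The concern.** A clinician managing a severe immune-related event will naturally turn to the section titled for such events, which is Section 14.3.3. There, a Grade 4 event is handled like a Grade 3 event: withhold, give steroids, and discontinue if the steroids cannot be tapered in time. A patient whose taper succeeds meets no stopping ground in that row. Under Table 5 the same patient has finished pembrolizumab for good.

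What is at stake is re-dosing after a life-threatening, drug-related event, and different handling of the same event from site to site. The efficacy analysis is not at stake. Section 20 defines PFS by radiographic progression or death, and Section 15.1 continues imaging for patients who stop treatment for reasons other than progression.

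**Working it through.** The plan states no figure to reproduce, so the check sets the provisions side by side and counts rows.

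**1. The event tested.** Grade 4, drug-related, non-hematologic, immune in nature, with no named row in Table 5.

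| Source | Action at Grade 3 | Action at Grade 4 |
|---|---|---|
| Table 5, catch-all row | Hold; restart on resolution to Grade 0-1 | Permanently discontinue |
| Table 5, note | Permanently discontinue on recurrence | Permanently discontinue if life-threatening |
| Table 10, last row | Withhold; discontinue if steroid taper fails | Same as Grade 3 |

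Table 13 in Section 17.3 defines Grade 4 as life-threatening, so the note under Table 5 reaches this event as well as the catch-all row does.

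**2. Does *withhold* mean something different from *discontinue*?** Table 10 does not say that treatment may restart. However, its action column is headed with both words as alternatives, and its last row uses both, with discontinuation as a further conditional step. Table 9, on pneumonitis, has a matching column. At Grade 2 it reads "Withhold pembrolizumab (MK-3475), may return to treatment if improves to Grade 1 or resolves within 6 weeks", and at Grades 3 and 4 it switches to discontinuing. The adjacent table therefore treats the two as separate actions.

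**3. Does the scope of Table 10 remove the overlap?** If the catch-all row counts as detail given elsewhere, Table 10 has almost no drug-related, non-hematologic dosing left to govern. If it does not count, both tables apply and disagree at Grade 4.

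**4. How usual is the Table 5 rule?** Rows in Table 5:
- Named non-hematologic: 9 (diarrhea/colitis; AST, ALT or bilirubin; type 1 diabetes or hyperglycemia; hypophysitis; hyperthyroidism; hypothyroidism; infusion reaction; pneumonitis; renal failure or nephritis).
- Catch-all: 1. Hematologic: 2. Total 9 + 1 + 2 = 12.

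Grade 4 action in the 9 + 1 = 10 non-hematologic rows:
- Permanently discontinue: 7 (colitis; hepatic, subject to its footnote; hyperthyroidism; infusion reaction; pneumonitis; renal; catch-all).
- Hold with possible restart: 2 (diabetes/hyperglycemia; hypophysitis).
- Continue with hormone replacement: 1 (hypothyroidism).
- Check: 7 + 2 + 1 = 10.

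The three exceptions are all endocrine. Withholding at Grade 4 is therefore a departure from Table 5's usual rule.

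**5. Patients who could be exposed.** Section 19.1 plans 62 patients on pembrolizumab and 31 on topotecan. Planned exposure runs from 62, with no crossover, to 62 + 31 = 93, with full crossover.

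**The case against.** The best reply is that the two tables can be read together. Table 10 never says that a Grade 4 patient may restart, and stopping for good also satisfies an instruction to withhold. Its steroid ground is not stated to be the only ground, and in a merged row it still does useful work for Grade 3. The sentence that introduces Table 5 itself uses withholding as an umbrella term, because the table then stops many of those events permanently. The structure also favors Table 5: Section 14.1 covers dose modification and is mandatory, Section 14.3 covers supportive care, and Table 10 is described as recommendations. The rechallenge entry in Table 13 refers to the dose modification guidelines, which matches the title of Table 5, "Dose Modification Guidelines for Pembrolizumab Drug-Related Adverse Events". On this reading Table 10 still has a purpose, since it supplies a steroid dose and taper that Table 5 lacks.

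Much of this stands. Table 5 is probably meant to govern, and a careful reader could reach that answer. What does not stand is the claim that nothing needs correcting. The umbrella usage in Section 14.1.1 does not carry over to a row that sets withholding and discontinuing apart. Precedence has to be inferred, because no sentence states it.

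The safeguards are real but partial. Section 14.3.3 asks for immediate discussion with the Study PI at Grade 2 or higher, but does not say which table to apply. Table 13 requires advance approval of rechallenge after a serious event that pembrolizumab may have caused, which presupposes that rechallenge can be considered. Section 16.2.1 requires discontinuation for unacceptable adverse experiences without defining them. These make wrongful re-dosing less likely; they do not settle which instruction is correct.

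**Conclusion.** The inconsistency is real and should be corrected. For the event described, Table 5 requires permanent discontinuation, and Table 10 requires withholding with one conditional ground for stopping. It is confined to one row of 12, at Grade 4, in a planned pembrolizumab population of 62 to 93. The documents give no frequency for these events, so no number of affected patients is claimed. The safeguards above lower the risk, and there is no effect on the primary analysis.

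The conclusion rests on two readings: that withholding in Table 10 is a different action from discontinuing, as its own layout and Table 9 indicate; and that the catch-all row applies to immune-related events, since nothing exempts them. A separate tension inside Table 5, between its note on life-threatening events and the rows that allow restart after Grade 4, is not part of this point.

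**What to change.** Split the last row of Table 10 in two and keep its supportive-care column for both parts.

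- **Grade 3:** withhold. Discontinue if the toxicity has not resolved to Grade 0-1 within 6 weeks of the last dose, or if steroids cannot be brought down to 10 mg or less per day of prednisone equivalent within 6 weeks. This copies Table 5. It adds the non-resolution ground that Table 10 lacks and removes the small mismatch between less than 10 mg and 10 mg or less.
- **Grade 4:** permanently discontinue, except where a specific Table 5 row provides otherwise. The exception is needed because, for example, the hypophysitis row allows treatment to continue with endocrine replacement.

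Add one sentence to Section 14.3.3: *Where Table 10 and Table 5 differ on pembrolizumab dosing, Table 5 governs.* Limit it to Table 10. A broader sentence would silently decide a separate conflict over Grade 3 enterocolitis, which Table 5 holds and Section 14.3.1 permanently discontinues; that needs its own correction.

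The cost is one split row and one added sentence in an amendment, with no change to sample size, visit schedule or analysis.
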